# STUDY PROCEDURES

# 1. Detailed Description

This study involves TRP depletion, evaluation of cognition, and the use of fMRI during cognitive and affective task performance both before and after estrogen or placebo treatment (PT). There will be four successful\* TRP depletion test sequences: two test sequences one week apart prior to ET or PT, and two sequences one week apart following approximately 6-weeks of double-blind ET or PT. Each TRP depletion test day will involve ingestion of 70 capsules. During one of each pair of tests, the 70 capsules will contain 31.5 g of lactose (sham depletion; for participants who are not lactose intolerant) or 31.5 g of microcellulose (sham depletion; for participants who have mild to moderate lactose intolerance), while during the other test they will contain a total of 31.5 g of amino acids, but no tryptophan (see below; Neumeister et al., 2004; Neumeister et al., 2005). The order of the tests (sham vs. active depletion) will be randomly assigned in double blind fashion by the research pharmacist. Imaging procedures will take place on each of the test days. Subjects will be required to remain at the Center for Human Phenomic Science (CHPS) for the entire Test Day except during the fMRI scan.\*\*

# TRP Depletion Tests:

Each of the four test days will begin in the morning, no later than 7:30 AM, following an overnight fast that begins at midnight and subjects will remain fasting until the end of the test session, approximately 8hours. Subjects will be admitted to a specially designated testing room on the CHPS/PCWBW and will remain in the test room for most of the session, but will be free to walk about the room and the CHPS/PCWBW, use the facilities, and drink water. They will be continuously monitored throughout the day by a trained research nurse, with a medical research investigator available at all times.

Baseline behavioral ratings, blood samples, and vital signs will be taken from 7:30 - 8:00 AM. Initial assessments include measurement of sleep quality (PSQI; test days 2 and 4 only), and hot flash severity (daily diary completed for previous 7 days). Mood will be evaluated using the HAM-D, BDI, POMS, STAI, PSS and VAS. Blood sampling in the morning on each test day will measure estradiol, progesterone, serum hormone binding globulin, DHEA, and baseline tryptophan (total and free) levels. Additionally, on the first test day only, one additional tube of blood will be drawn to examine genetics of estrogen synthesis and metabolism and genes for neurochemicals/systems modulated by estrogen and Version: November 28, 2016 IRB APPLICATION page 18 of 35

other sex hormones. Functional polymorphisms to be examined include but are not limited to TPH2-703 G/T, 5HTTLPR SLC6A4, HTR1A-1019 C/G, rs6295, HTR2A-rs7997012. These functional polymorphisms are hypothesized to be linked to regulation of mood and/or aspects of cognition in human subjects. However, estrogen has pronounced effects upon multiple neurotransmitter systems and receptors involved in the regulation of cognition and mood including, acetylcholine, dopamine, glutamate and norepinephring in addition to serotonin. Therefore, we stipulate herein and in the subject consent form that we will limit all genetic analyses to those specifically related to estrogen and its neurotransmitter system targets as they relate to the regulation of mood and cognition. Following these baseline measurements, subjects will begin ingesting the 70 capsules of amino acid mixture or lactose/microcellulose sham. They will have approximately 30 minutes to ingest the capsules (8:00 – 8:30 AM), which will help to minimize discomfort. However, we anticipate the ingestion of capsules will begin prior to 8:00 AM, thus given each subject longer than 30 minutes to complete this task. In addition, a nurse will be present to insure subjects' safety during the process.

Please note that although ingesting 70 capsules may sound taxing, all 8 women who began the study to date at Yale from our pilot study completed it. Thus, each of them took 70 capsules on four different test days. Because the capsules are ingested with a research nurse and experimenter present, participants tend to pace themselves by engaging in conversation between swallows and find the unpleasantness of the situation minimized. Even so, the average time needed to ingest all capsules has been only 25 minutes. According to one participant, the idea of 70 capsules is worse than actually taking them. Feelings of fullness and transient, but mild, nausea were the most common complaints. We switched to this particular method of TRP-D from that used in our previous studies (Epperson et al., 2006; Amin et al., 2006b) as our previous method required that women ingest 20 capsules in addition to 8 ounces of an amino acid drink. Despite flavoring the drink with chocolate syrup, it was gritty and unpleasant.

Approximately 5.5 hours following ingestion of the 70 capsules, participants will repeat evaluations of mood and undergo cognitive testing (1:30 - 2:00 PM). Immediately prior to the fMRI scan (2:30 PM), a second blood draw will be conducted to measure changes in free and total tryptophan. Participants will then be escorted to CAMRIS for performance of cognitive tasks while in a 3T MR scanner. Immediately prior to entering the scanner, all participants will submit a urine sample for toxicology and urine pregnancy tests, as required by CAMRIS. The scan will begin approximately 6.5 hours following ingestion of capsules. After the end of the test session, a regular diet will be resumed. We will provide a light lunch to all participants prior to discharging them at the end of the test day.

The second TRP depletion test will be administered 1-week after the first. If subjects were randomized to receive the capsules filled with 31.5 g of lactose/microcellulose (sham depletion) during the first depletion sequence, they will receive capsules filled with amino acids (active depletion) during the second sequence (and vice versa). The clinicians conducting the study and the subjects in the study will be blind to which mixture the subject is receiving in the capsules. Following approximately *6-weeks* of ET, another pair of test days will be scheduled one week apart, one sham and one active.

\*In cases where participants do not fully complete a test day before being randomized to the study drug, they will have the option to repeat the unsuccessful test day in full.

\*\*If subjects cannot commit to completing test days Monday through Friday, there is an option to complete scans on weekends. These participants will not be utilizing the services of the CHPS and will instead be monitored by a study MD during their test day instead of CHPS nurse. These women will report to [name] and will complete the test day exactly as described above, with the

exception of spending the test day at the CHPS. They will be asked to remain in the PCWBW office until they are brought to CAMRIS for the afternoon testing session. A private room with a comfortable chair for resting during the test day will be provided to the subject who will then have their vital signs and bloodwork completed by the onsite study MD. A meal of an apple, turkey sandwich, and drink will still be provided to all participants upon completion of their test day. These items will be purchased at Subway or Wawa.

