Note 2: Women who undergo the repeat FSH blood test will be enrolled if their levels are  $\geq$  30. Women will not be required to repeat all admission procedures unless they report experiencing a life event which would impact their mental or physical health and well-being. The PI will make the final determination regarding what, if any, screening procedures need to be repeated.

Note 3: Women on localized estrogen treatments who show elevated systemic estrogen levels will not be enrolled. Instead, they will need to discontinue use for 1 month and then have their estrogen levels retested with an additional blood draw. PI will have the final decision regarding eligibility.

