#### STUDY DESIGN

	Subject met at CHPS/PCWBW and initial assessments conducted; this includes the blood draw conducted by research nurse to determine estrogen, progesterone, serum hormone binding globulin, DHEA, and
7:30 AM	tryptophan levels
8:00 AM	Subject begins ingestion of 70 capsules with nurse present
8:30 AM	Subject completes ingesting capsules
2:00 PM	Assessments and memory testing
	Blood draw conducted by research nurse to determine change in free and
2:30 PM	total tryptophan
3:00 PM	Begin fMRI scan
3:45 PM	Post-scan recognition test
4:00 PM	Subject given meal and discharged after seeing a physician

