#### 7. Investigator's Risk/Benefit Assessment

This study presents moderate risk to the participant. Effective screening will be used to eliminate subjects who will be placed at a greater risk. This includes a medical and psychiatric history, physical

examination, and laboratory studies. No subject will be enrolled in the study unless they provide written documentation of having had a normal gynecologic examination, PAP smear and mammogram within the past year. This will be required of all women taking estrogen while they are participating in the tryptophan depletion study. The careful psychiatric evaluation will rule out any psychiatric conditions that could affect the subject's suitability for the study.

In addition, if a subject is pregnant, or planning to become pregnant, they will not be allowed to participate in this study. Hormone replacement therapy and the tryptophan depletion paradigm are not approved for use and administration during pregnancy and breastfeeding. Women who can have children must have a negative pregnancy test prior to enrolling in this study and must practice a medically accepted method of contraception during the entire study; this includes abstinence. Medically accepted methods of contraception will be discussed with each subject.

Subjects will be closely followed during the study by an experienced clinical research team. Careful monitoring of cardiovascular and behavioral parameters repeatedly and frequently during each test session will allow objective evaluation of the effects of the test. Prior experience with this test includes no significant adverse effects. In addition, all tests are done on a specially designed and staffed research unit with constant medical and nursing supervision. This unit has completed a large number of studies of this type and is specifically designed and equipped to support such studies. The principal investigator will be on call at all times to evaluate any problems that arise.

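### On every test day the urine pregnancy test comes about 6 to 6.5 hours after the capsules are finished, so a pregnancy missed at screening or begun since the last test is found only after that day's capsules.

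*Combined protocol and SAP*

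**What the plan says.** All references are to the combined protocol and SAP.

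**The bar.** Key Exclusion Criteria, item 16, excludes pregnant women and limits the item to perimenopausal women. The Investigator's Risk/Benefit Assessment repeats the bar and gives a reason: "Hormone replacement therapy and the tryptophan depletion paradigm are not approved for use and administration during pregnancy and breastfeeding". For women who can have children, that section also requires a negative pregnancy test before enrolment and accepted contraception for the whole study.

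**The screening test.** The end of Study Instruments lists a urine pregnancy test during screening for perimenopausal women. Key Inclusion Criteria, item 7, lets a woman with FSH below 30 have a second draw 3 to 9 months after the first. On her return, Note 2 to the exclusion criteria says: "Women will not be required to repeat all admission procedures unless they report experiencing a life event". The PI decides which procedures, if any, are repeated.

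**The test day.** TRP Depletion Tests describes the morning block: "Baseline behavioral ratings, blood samples, and vital signs will be taken from 7:30 - 8:00 AM". The blood analytes are listed too: "Blood sampling in the morning on each test day will measure estradiol, progesterone, serum hormone binding globulin, DHEA, and baseline tryptophan (total and free) levels". Then come the capsules: "They will have approximately 30 minutes to ingest the capsules (8:00 – 8:30 AM), which will help to minimize discomfort". The pregnancy test follows in the afternoon: "Immediately prior to entering the scanner, all participants will submit a urine sample for toxicology and urine pregnancy tests, as required by CAMRIS".

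**The concern.** An exclusion protects against an exposure only if the check comes before the exposure. Here the test-day check is placed to meet the scanner facility's requirement, and it follows the capsules on all four test days. The section that says depletion is not approved in pregnancy and the section that sets the test-day order do not fit together.

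At stake is a participant-safety rule, not an estimate, a sample size or an error rate. A missed case would be rare, but it is the case the exclusion was written for. The day's capsules cannot be assumed harmless in advance either: each pair of days holds one active and one sham day in random order, and the participant and the clinicians conducting the study are blind to which is which.

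**Working it through.** **1. The plan's own interval.** TRP Depletion Tests says: "The scan will begin approximately 6.5 hours following ingestion of capsules". The schedule under Study Design has capsules begun at 8:00 AM and finished at 8:30 AM, a second blood draw at 2:30 PM, and "Begin fMRI scan" at 3:00 PM.

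- Scan minus end of capsules: 15:00 − 8:30 = 6.5 h. This reproduces the stated figure.
- Scan minus start of capsules: 15:00 − 8:00 = 7.0 h.

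**2. The pregnancy test.** The text places it after the 2:30 PM draw and just before the scanner, so between 2:30 and 3:00 PM.

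- From the end of capsules: 14:30 − 8:30 = 6.0 h to 15:00 − 8:30 = 6.5 h.
- From the start of capsules: 14:30 − 8:00 = 6.5 h to 15:00 − 8:00 = 7.0 h. It is longer if ingestion begins before 8:00, as the plan expects.

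**3. Is anything listed earlier that day?** The morning block consists of ratings, blood samples and vital signs. The analytes are hormones, binding globulin and tryptophan, with no pregnancy marker. The Study Design schedule lists no morning urine test, but it also omits the afternoon one, so its silence carries little weight. The detailed text of TRP Depletion Tests is the evidence.

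**4. Age of the latest pregnancy result when the capsules are taken.** Each test day includes its own test, so the age differs by day.

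| Test day | Previous pregnancy test | Age of that result |
|---|---|---|
| 1 | Screening | No maximum stated; 3 to 9 months or more is possible on the repeat-FSH path if the test is not repeated |
| 2 | Test day 1 | About 1 week |
| 3 | Test day 2 | About 6 to 7 weeks (about 6 weeks of patch treatment plus the time from test day 2 to its start) |
| 4 | Test day 3 | About 1 week |

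**5. How often the capsules are the depletion mixture.** One day of each pair is active, so 2 of 4 days, or half. With random order, taken as 1:1, test day 1 is active with probability 0.5.

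**The case against.** The strongest reply is that the test-day test is one safeguard among several. A negative test is required before enrolment, contraception is required throughout, and age 48 to 60 with FSH of at least 30 makes pregnancy unlikely. Both pre-treatment test days also carry a pregnancy test before randomisation to estrogen. All of this stands. It limits the risk to a pregnancy that screening missed or that began despite contraception, but it does not change the order on the test day.

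A reader might infer several stronger points that the documents do not support:

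- **That the exclusion has no protective force.** The enrolment test and the contraception requirement contradict this.
- **That a result 3 to 9 months old could apply on all four days.** It can apply only on test day 1.
- **That Note 2 waives the pregnancy test.** It says only that not all procedures must be repeated and leaves the choice to the PI. The gap is silence, not a waiver.
- **That every such woman would have received depletion.** On sham days she has swallowed lactose or microcellulose.
- **That toxicology raises the same problem.** The toxicology criterion applies at recruitment. No section bars depletion after a positive test-day toxicology result or says that such a result cancels the scan.
- **That late testing loses data.** If a positive pregnancy test cancels the scan, it does so at 7:30 AM as well as at 2:30 PM. Earlier testing would spare the capsules and part of the fast, but it would not recover the scan.

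**Conclusion.** The point holds for pregnancy testing only. On all four test days the capsules precede the only listed pregnancy test by 6.0 to 6.5 hours, counted from the end of ingestion. The practical gap is mainly for perimenopausal women on test day 1, where the age of the screening result has no limit, and on test day 3, where the last result is about 6 to 7 weeks old. On days 2 and 4 it is about one week old.

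This rests on two assumptions: that the morning block in TRP Depletion Tests is complete with respect to pregnancy testing, and that on the repeat-FSH path the PI may leave the screening pregnancy test unrepeated. The documents give no pregnancy rate, so no expected number of cases is offered; the risk is judged low. The change is still worth making, because it lets an existing exclusion act before the exposure it names, at almost no cost.

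**What to change.** - **Reconcile the timing.** Bring TRP Depletion Tests and the Study Design schedule into line with Key Exclusion Criteria item 16 and the Investigator's Risk/Benefit Assessment on when the pregnancy test is done relative to the capsules. One way is to collect the already planned urine pregnancy sample in the 7:30 AM baseline block for women who can become pregnant, and to keep the scanner-site test if the facility needs its own. How a positive result is handled is for the sponsor to state.
- **Close the re-entry gap.** State in Note 2 that the pregnancy test is repeated when a woman re-enters after a repeat FSH draw.

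The cost is schedule wording and at most one extra urine dipstick per test day for these women, plus one test at re-entry. The morning block is short and ingestion may start before 8:00 AM, so the sample would need to come early in it. Sample size and analysis are unaffected.

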## Amino Acid Mixture:

According to a protocol successfully employed at the National Institutes of Health (NIH) with no reported adverse effects (Neumeister et al., 2004; Neumeister et al., 2005), an amino acid mixture will be prepared by combining amino acid powders into 70 capsules to be swallowed by the subject on the morning of each Test Day. Ingesting this tryptophan-free mixture stimulates protein synthesis, which depletes plasma TRP levels and causes the amino acids to compete with tryptophan to cross the blood-brain barrier, resulting in an overall decrease in brain tryptophan levels and, therefore, serotonin. In order to maintain the double-blind condition of each TRP depletion test, identical-appearing capsules containing either the amino acid mixture or placebo (31.5 g of lactose or microcellulose) will be given. The amino acids in this mixture are:

L-Isoleucine (4.2 g), L-Leucine (6.6 g), L-Lysine (4.8 g), L-Methionine (1.5 g), L-Phenylalanine (6.6 g), L-Threonine (3.0 g), L-Valine (4.8 g)

A pharmacist affiliated with the CHPS prepares the amino acid mixture. The pharmacist prepares the mixtures (both active and placebo) in advance batches, which will be kept in a temperature-controlled location (15-30 degrees Celsius) at Investigational Drug Service until a participant is scheduled for a study test day. The 70 capsules are then sent as a kit to the principal investigator/CRC/study nurse to dispense as part of the study challenge. The amino acids fall under guidelines for which there are adequate data demonstrating their safety. The amino acids are manufactured by the following companies:

- L-Isoleucine, L-Leucine, L-Phenylalanine, L-Threonine, L-Valine: Fagron
- L-Methionine: Spectrum (we also have L-Phenylalanine and L-Threonine from Spectrum)
- L-Lysine: Research Products International
- Capsules: Total

Each of the seven amino acids comes with a certificate of analysis indicating that the substance is nonpyrogenic, and that it has been inspected and meets the company's quality assurance standards prior to shipping. In addition, we have received an IND (#74,972) from the U.S. Food and Drug Administration, which approved the use of amino acids in this study. A separate IND specifically for the amino acids was not necessary.

# **Imaging Parameters**

All fMRI scans will take place at the Center for Advanced Magnetic Resonance Imaging & Spectroscopy (CAMRIS) at the University of Pennsylvania School of Medicine. Whole-brain imaging data will be

acquired on a Siemens 3.0 Tesla Trio system. For structural whole brain images, the first scan is a sagittal localizer, followed by a T1 scan oriented in the axial-oblique dimension, parallel to the anterior commissure-posterior commissure (AC-PC) line (24 slices, repetition time = 300 ms, matrix size = 256 x 256, field of view = 220 x 220 mm). A three-dimensional high-resolution spoiled gradient scan will also be conducted (176 slices, repetition time = 2530 ms, matrix size = 256 x 256, field of view = 256 x 256 mm). Functional whole-brain images will be acquired using a gradient echo T2\*-weighted echoplanar imaging scan (repetition time = 1500 ms; echo delay = 30 ms; flip angle = 80°; field of view = 220 x 220 mm). Measurements of cerebral blood flow at rest will involve scanning using the MRI arterial spin labeling (ASL) perfusion technique. Ten AC-PC aligned slices will be acquired for both the top and bottom parts of the brain (10 slices;  $4 \times 4 \times 6 \text{ mm}^3$ ; echo delay = 20 ms; 80 images). A proton density (PD) weighted image will be acquired using the same sequence as perfusion.

# Randomization to Estrogen Treatment (ET) or Placebo Treatment (PT)

After completing the first two TRP depletion test sequences, participants will be randomized to receive either treatment with 17β-estradiol (Vivelle Dot® 0.10 mg/day) or a look-alike placebo patch for a total of 8 weeks. The research pharmacist who is responsible for dispensing the estrogen or placebo patches will also be responsible for the randomization of all subjects together with the statistician on the study. Randomization will be blocked and stratified. We will use a block size of 3 to be able to maintain a 2:1 ratio of estrogen to placebo within each stratum. To stratify randomization based upon time since last menstrual period by tertiles (1st=0-40 mos; 2nd=40-80 mos; 3rd=80-120 mos), we will prepare separate randomization tables for each stratum. The research pharmacist, PI, and research project manager will know to which group the subject has been randomized. The research pharmacist, PI or research project manager can be reached at any time should it become necessary to unblind a study participant immediately. The subject and all other study-related personnel (clinicians, raters, fMRI technicians, etc.) will be blind to subject assignment.

For the peri- and post-menopausal women participating in our previous tryptophan depletion/estrogen study (Amin et al., 2006b), mean baseline estradiol level was 31.72 pg/ml. With the 0.10 - 0.15 mg/d estradiol dose, mean estradiol levels were 96.33 pg/ml. Thus, our goal is to achieve a similar increase in estradiol in subjects participating in the present study. These doses are higher than the lowest available and may be higher than the lowest effective dose, which is the standard in clinical practice. However, in this experimental context, it is necessary to have a significant increase in plasma estradiol level in order to evaluate estrogen's effects. In addition, the standard dose in clinical practice is recommended for long-term ET. The proposed short-term ET regimen (chosen to more closely mimic the cyclic regimens currently recommended) is not likely to be associated with as significant risks as long-term ET. In our previous study, although women with greater time since LMP were found to have lower pre-treatment estradiol levels, the relationship between time since LMP and estradiol was less negative following ET, suggesting increased similarity among participants. Nevertheless, we will control for both age and plasma estradiol level when examining effects of time since LMP.

Following completion of approximately 6 weeks of ET or PT, the subjects will participate in the last two TRP depletion test sequences (one sham and one active depletion). Upon completion of the 4th test day (or use of estrogen for at least 2 weeks in those who drop out), all subjects will be debriefed regarding their active vs placebo patch status and subjects randomized to ET will take Prometrium (micronized progesterone USP encapsulated with peanut oil) 200 mg daily or medroxy progesterone 5 mg/d (for women with peanut allergies) for 12 days. Prometrium and medroxy progesterone are USFDA approved for antagonism of estrogen effects on the endometrium in women taking hormone treatment (HT). According to a review of studies of oral progesterone in menopausal women, use of progesterone,

the progestational steroid produced by the human corpus luteum, minimizes side effects seen with synthetic progestins (McAuley et al., 1996). Long-term protection of the endometrium by Prometrium given as 200 mg/day for 12 days/month or medroxy progesterone given as 5 mg/d has been established (Gibbons and Thorneycroft, 1999). Oral micronized progesterone at a dose of 200 mg/ day is well-tolerated, with the only specific side effect being mild and transient drowsiness. Those women who would like to continue hormone therapy will be prescribed 3 additional months of estrogen (as well as an additional Prometrium treatment for women who have an intact uterus) and then referred to their gynecologist for continued treatment. The participant or her insurance company will be responsible for covering the cost of the additional treatment. Those women who wish to discontinue their HT will do so after cycling themselves with Prometrium or medroxy progesterone for 12 days. After the 12 days of Prometrium or medroxy progesterone with the Vivelle patch, women will discontinue both hormones.

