#### OBJECTIVES

**Specific Aim 1:** To replicate and extend our previous behavioral findings of an interaction between ET and TRP-D on verbal memory in a group of early menopausal women randomized to receive ET (n=28). In a previous behavioral study of TRP-D and ET in healthy menopausal women (Amin et al., 2006b), we observed that TRP-D interfered with verbal memory to a lesser extent following ET than before. *In a new sample of women, we again hypothesize* (**H1.1**) *that paragraph recall performance and verbal paired-associates learning will decline as a result of TRP-D, but that ET will attenuate this decline.* In our previous study, we also found that length of hypogonadism (measured by months since last

menstrual period) was significantly associated with waning verbal memory performance. However, we did not have sufficient power with 18 women to detect whether the magnitude of ET effects differed based on length of time since menopause. *In this larger sample of 28 women, we hypothesize* (H1.2) *that women who have more recently experienced menopause will benefit more from ET than later menopausal women.* 

**Specific Aim 2:** To evaluate the extent to which effects of ET and TRP-D on verbal working memory are mediated through the dorsolateral prefrontal cortex. Previous neuroimaging studies have associated ET with improved working memory performance and increased dorsolateral prefrontal cortex (DLPFC) activation (Duff & Hampson 2000; Shaywitz et al., 1999). However, it is unclear whether TRP-D has an effect on working memory (Harrison et al., 2004; Riedel et al., 2003). It is hypothesized (**H2.1**) that ET will increase DLPFC activation during working memory more so than PT, but there will be no effect of TRP-D and no interaction between estrogen and serotonin effects in either the ET or PT groups. Very few fMRI studies have examined the impact of practice or rescanning on behavioral measures or the BOLD response during cognitive tasks. We seek to fill that void with the proposed study by including a placebo arm. Since submission of the A2 application, we have obtained test-retest data from our MR colleagues ([name], Ph.D.) demonstrating that with our new sample size of 28 women receiving ET and 14 women receiving placebo we can adequately test our hypothesis regarding ET and TRP-D effects on DLPC activation during the proposed working memory task.

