#### 5. Early Withdrawal of Subjects

Early withdrawal of subjects may occur for the following reasons:

- 1. If the subject fails to return for visits.
- 2. Failure to locate the subject.
- 3. The subject withdraws their consent for participation.
- 4. The PI determines that the subject is no longer eligible for participation in the study.

A subject can withdraw their consent for participation in this study by contacting the study PI and or the research staff personnel who is following them in the study via telephone and informing them of their decision. In this case it would be preferable if the subject is willing to come in to the office for a debriefing regarding whether or not to continue estrogen treatment under the care of their personnel physician. If this is not possible, then the PI will speak with the subject by telephone to conduct this debriefing and find out whether or not the subject plans to stay on estrogen treatment. The subject's decision to withdraw and their disposition upon withdrawing from the study will be recorded in their research chart.

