# 3. Method for Assigning Subjects to Groups

After completing the first two TRP depletion test sequences, participants will be randomized to receive either treatment with 17β-estradiol (Vivelle Dot® 0.10 - 0.15 mg/day) or a look-alike placebo patch for a total of 8 weeks. The research pharmacist who is responsible for dispensing the estrogen or placebo patches will also be responsible for the randomization of all subjects together with the statistician on the study. Randomization will be blocked and stratified. We will use a block size of 3 to be able to maintain a 2:1 ratio of estrogen to placebo within each stratum. To stratify randomization based upon time since last menstrual period by tertiles (1st=0-40 mos; 2nd=40-80 mos; 3rd=80-120 mos), we will prepare separate randomization tables for each stratum. The research pharmacist, PI, and research project manager will know to which group the subject has been randomized. The research pharmacist, PI or research project manager can be reached at any time should it become necessary to unblind a study participant immediately. The subject and all other study-related personnel (clinicians, raters, fMRI technicians, etc.) will be blind to subject assignment.

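### A constant, published 2:1 block of 3 makes up to about 40% of assignments deducible from earlier ones; concealment is weak and the staff blind is not protected.

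*Combined protocol and SAP*

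**What the plan says.** Randomisation to ET or placebo follows the second test day and is stratified into three bands of time since last menstrual period. The same rule stands under METHODS, Method for Assigning Subjects to Groups, and under STUDY PROCEDURES, Randomization to ET or PT: "We will use a block size of 3 to be able to maintain a 2:1 ratio of estrogen to placebo within each stratum". For the three bands, "we will prepare separate randomization tables for each stratum". The planned total is given under OBJECTIVES, Specific Aim 2: "new sample size of 28 women receiving ET and 14 women receiving placebo".

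The research pharmacist, the PI and the project manager know every assignment. For everyone else: "The subject and all other study-related personnel (clinicians, raters, fMRI technicians, etc.) will be blind to subject assignment".

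The last two test days come about six and seven weeks after treatment starts ("two sequences one week apart following approximately 6-weeks of double-blind ET or PT"). After each woman's fourth test day, "all subjects will be debriefed regarding their active vs placebo patch status and subjects randomized to ET will take Prometrium". The protocol does not say who gives this debriefing on completion, or whether the result is kept from testers and raters.

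The PI has the final word on enrolment in some cases (Key Exclusion Criteria, item 10 and Notes 2 and 3). One listed reason for early withdrawal is: "The PI determines that the subject is no longer eligible for participation in the study".

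**The concern.** A block of 3 with exactly one placebo leaves little to chance. Once the placebo woman in a block is known, the rest of that block is ET; once two ET women are known, the third is placebo. Completed assignments come to light during the trial, one woman at a time, and two roles know them from the start.

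Two things are at stake. The first is concealment: a person who can foresee the next arm should not also be able to decide whether the next woman goes forward. The second is the blind: a tester or rater who learns earlier results could infer the arm of a woman still on treatment. With only 14 placebo women planned, a few such cases carry weight.

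**Working it through.** **Planned figures.** 28 + 14 = 42 women; 42 × 2/3 = 28 ET and 42 × 1/3 = 14 placebo, so the stated sizes agree with 2:1.

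**Forced positions in a known block of 3.** The orders EEP, EPE and PEE are equally likely.
- Position 1 is never forced.
- Position 2 is forced only if position 1 was placebo: probability 1/3.
- Position 3 is always forced.
- Expected forced positions: 0 + 1/3 + 1 = 4/3 of 3, or 44.4%.

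**Scaled to the trial.** Stratum sizes are not stated; assume 14 each, which is four full blocks plus two positions.
- Per stratum: 4 × 4/3 + 1/3 = 17/3 = 5.67.
- Three strata: 3 × 17/3 = 17, and 17/42 = 40.5%.
- Several other splits of 42 give 41-44%.

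**Best-guess accuracy.** Positions 1, 2 and 3 give 2/3, 2/3 and 1. Over complete blocks this is (2/3 + 2/3 + 1)/3 = 77.8%. In strata of 14 it is (4 × 7/3 + 4/3)/14 = 76.2%. Always guessing ET gives 66.7%.

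**Who can use this, and when.** The PI and project manager know earlier assignments without delay, so the 40.5% applies to them before randomisation. For other staff the route is the debriefing, about 7-8 weeks after randomisation. The accrual period is not stated. Two lengths that the protocol mentions serve as a range: the 2-year grant (OBJECTIVES, note on exploratory aims) and the 5-year period (RESOURCES). A simulation of 42 women, 14 per stratum, with uniform accrual and no dropout, gives the share of assignments that are certain:

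| Point in time | 2-year accrual | 5-year accrual |
|---|---|---|
| Before randomisation | 17-19% | 29-30% |
| By her own Test Day 3 | 33-36% | 37-39% |
| By her own Test Day 4 | 37-41% | 39-41% |

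Each range covers a lag of 8 to 7 weeks. All entries are ceilings: they assume that staff learn every debriefing result, the stratum and the order of randomisation.

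**The alternative.** Take an equal random mix of blocks of 3 and 6 in strata of 14, and a guesser who knows all earlier assignments and the two possible sizes but not their order. Simulation gives 8.6% of assignments certain and a best-guess accuracy of 74%.

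**The case against.** The strongest reply is that 40% is a ceiling and the leak to blinded staff is hypothetical. Much of this stands.

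- **Lag.** A reader might infer that about 40% of assignments can be foreseen in advance through the debriefing. They cannot. At 2-year accrual the mean gap within a stratum is 104/14 = 7.4 weeks. With exponential gaps and a 7-week lag, the chance that even the preceding woman has been debriefed is exp(−7/7.4), about 39%. At 5 years (260/14 = 18.6 weeks) it is about 69%.
- **Blind.** A reader might infer that the staff blind must fail. The protocol says that participants are debriefed, not raters, clinicians or technicians. The one place that names a debriefer, Early Withdrawal of Subjects, names the PI, who is already unblinded. The test-day timetable has each woman see a physician before discharge, but does not place the debriefing there or say that this physician is blinded.
- **Staff choices before randomisation.** Repeating an incomplete test day is the participant's option. The only staff decision shown is the PI's on eligibility. For that route the debriefing adds nothing; the predictable block is the defect.
- **Impact.** A reader might infer that biased depression ratings or memory testing would undermine Aim 2. Its outcome is DLPFC activation on fMRI, so that link is not supported. Verbal memory belongs to Aim 1, which is framed within the ET women, and the sham/active order is assigned separately.
- **Remedy.** Best-guess accuracy falls only modestly, and the PI and project manager still know past assignments. Both are true. But the share that can be known with certainty falls by about four fifths, and knowing the past then says much less about the next assignment.

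What remains is that the protocol prints the block size, reveals results while the trial runs, gives ET women a visible further treatment, and sets no barrier between this and the staff declared blind.

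**Conclusion.** The point holds as a weakness in concealment and an unprotected blind, not as a demonstrated failure of either. Someone who knows the earlier assignments can deduce up to about 40% (17 of 42, assuming 14 per stratum). That applies directly to the PI, who also holds eligibility decisions, and to the project manager. For staff declared blind the ceiling is about 17-30% before randomisation and 33-41% by Test Days 3-4, and it depends on their learning debriefing results or seeing who receives a progestin. These timing figures rest on assumed accrual of 2 to 5 years, uniform entry, no dropout and a lag of 7-8 weeks; the documents give neither stratum sizes nor an accrual rate. The change is worth making because it costs little.

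**What to change.** In both randomisation paragraphs (METHODS, Method for Assigning Subjects to Groups; STUDY PROCEDURES, Randomization to ET or PT):

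1. Replace the constant block of 3 with randomly ordered blocks of 3 and 6, keeping 2:1 in each stratum. Remove the block sizes from the protocol and hold them in a document open only to the pharmacist and statistician. Certain assignments fall from about 40% to about 8-9%; best-guess accuracy falls from 78% over complete blocks (76% in strata of 14) to 74%.
2. State that the debriefing is given by a person who is already unblinded, and that patch status stays out of the records that testers and raters use until the last woman in that stratum has finished Test Day 4.

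The timing of the debriefing and the progestin treatment do not change. The cost is new randomisation tables and a short protocol edit. The downside is that the 2:1 balance within a stratum may be off by one or two more women than with blocks of 3.
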